The study is designed to be a parallel group trial, with participants evenly allocated to each study condition, using a superiority framework.

Methods: Participants, Interventions, and Outcomes

Methods Overview

We will conduct a 3-week web-based RCT of U.S. adults who currently use LCCs. In this study, LCC warnings on packs will be electronically presented to participants over time to determine if newly developed LCC warnings increase quit intentions compared to FDA proposed text-only warnings and a control condition (in which participants do not see LCC packs or warnings.) We will apply a daily diary methodology to present LCC warnings on packs to participants over time. Qualtrics will contact, screen, consent and administer the survey. To enroll participants, Qualtrics will screen participants using our inclusion criteria and measures and invite eligible participants to enroll in the study. To collect at least 750 quality completes we anticipate enrolling up to 3,000 people.

At the beginning of the baseline survey (day 0), participants will first consent to participate in the study and then complete a questionnaire about their tobacco use and behaviors (e.g., intentions and quit attempts) and other measures of interest. At the end of the baseline questionnaire, survey software will randomly assign participants to one of the 3 study conditions. The three study conditions are: 1) Newly developed warnings (the six most effective warnings developed by the study team), 2) FDA proposed text-only warnings or 3) No warnings (control condition) in which participants will not see warnings. Participants will be contacted via email each day (at approximately 6am) to invite them to complete the survey for that day of the study protocol.

For subsequent days (days 1-6, 8-13, 15-20) participants will be contacted and asked to complete a daily survey which will assess their previous day use of LCCs, as well as cigarettes and e-cigarettes. During these daily surveys, participants assigned to condition 1 or 2 (i.e., the warning conditions) will view an image of a little cigar and cigarillo package with a warning according to the participant's condition. Participants within each warning condition will view a total of 6 different warnings over the course of 6 days each week, this will be repeated 3 times during the study, resulting in a total of 18 exposures. Participants will be required to view the warning for at least 5 seconds before answering questions.

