Additional intervention details

Participants can withdraw from the study if they choose by no longer responding to the survey links and may withdraw their data by contacting the UNC study team.

Multiple strategies have been implemented to maximize adherence to the trial protocol, including reaching out to participants via email with invitations and reminders each day, compensating them based on completion of the most important questionnaires.

There is no relevant concomitant care or interventions that are permitted or prohibited during the trial.

Outcomes

[figure not shown]
Primary

- LCC guit intentions at post test (day 21)
 - Average quit intention score measured by survey, Quit intention measured with 3 questions, the final
 quit intention score is a mean of the response to the 3 questions, on a scale of 1 to 4, where 1 indicates
 low intention to quit, and 4 indicates a high intention to quit.

Secondary

- Number of LCCs smoked in past day (each day)
 - Measured daily by survey
- Number of days smoked LCCs in past week (days 7, 14, and 21)
 - Measured weekly by survey
- Number of LCCs smoked in the past week (days 7, 14, and 21)
 - Measured weekly by survey
- Butting out LCCs (days 7, 14, and 21)
 - Measured weekly by survey
- Forgoing LCCs (days 7, 14, and 21)
 - Measured weekly by survey
- LCC quit attempts (days 7, 14, and 21)
 - Measured weekly by survey
- LCC quit intentions (days 7 and 14)

- Average quit intention score measured by survey, Quit intention measured with 3 questions, the final
 quit intention score is a mean of the response to the 3 questions, on a scale of 1 to 4, where 1 indicates
 low intention to quit, and 4 indicates a high intention to quit.
- Self-reported learning (day 21) (only conditions 1 and 2)
 - Measured by survey. Self-reported learning measured with one item on a 1 to 5 scale, where 1 indicates no learning, and 5 indicates a great deal of learning from the warnings in the study.

Sample Size

The sample size is based on quit intentions effect sizes from an RCT comparing graphic cigarette warnings to text only warnings (Brewer, 2016). Based on the effect size observed in that study, we would have 80% power at α =0.05 to detect a small change in differences between our groups (f=0.12).

Recruitment

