We are working with Qualtrics research services to conduct this study and enroll participants from one of the panel providers that they work with. Qualtrics has access to high quality research panels across the US. They are able to leverage these panels to provide timely and reliable data collection to UNC and other research universities. We have high confidence that Qualtrics will be able to meet our recruitment goals.

Compensation Plan

Qualtrics will manage participant incentives. Participants in studies conducted by Qualtrics receive an incentive based on the length of the survey and their specific profile. The types of rewards vary and may include cash, airline miles, gift cards, redeemable points, sweepstakes entrance and vouchers. Participants who complete only the screening survey will receive a small incentive. For this study, participants who complete the baseline, 6 of the daily message surveys, at least one of the weekly surveys (day 7 or day 14), and day 21 will receive an incentive. Participants who complete only a few of the surveys but do not satisfy the criteria above will not receive an incentive.

Methods: Assignment of interventions

Allocation and Blinding

Participants will not be informed specifically about the possible interventions that they may be assigned to. Researchers will not be blinded to the condition that participants had been assigned to, however all outcome measures will be assessed via online survey. At the end of the baseline survey, survey software will randomly assign participants to one of the three study arms. Participants will have an equal chance of being randomized to each study arm.

Methods: Data collection management, and analysis

Data collection methods

Data collection will be conducted using Qualtrics web survey platform, questionnaires and references for measures can be found in the study measures document. Where possible, the measures used are previously developed and validated measures. Multiple strategies have been implemented to maximize adherence to the trial protocol, including reaching out to participants via email with invitations and reminders each day, and compensating them based on completion of the most important questionnaires.

Screener

Qualtrics will use invite potential participants to complete the screening survey and people who are eligible will be invited to complete the baseline survey. The screener is used to assess participant eligibility and collect demographic data.

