Baseline Survey: Day 0

- Eligible participants will be invited to participate in the study and complete the baseline survey to enroll
- The first part of the baseline survey will be a consent form with an agreement to participate in the study
- The baseline survey contains baseline tobacco use questions (e.g., motivation to quit, previous year LCC quit attempts, nicotine dependence, etc.).

 At the end of the baseline questionnaire, survey software will randomly assign participants to one of the 3 study conditions

Daily Surveys: Days 1-6, 8-13, and 15-20

- There are 18 daily surveys, which align with each participant's condition. Participants in conditions 1 and 2 will be shown stimuli (in accordance with their assigned condition) and condition 3 will not see any stimuli. Participants will stay in their condition throughout the study. Depending on the day, participants will see a different message
- Daily surveys will be sent out at 6am EST and will close at 2am EST (gives west coast until 11pm to complete surveys). There will be a reminder email sent in the afternoon.

Weekly Surveys: Days 7, 14

- Weekly behavior surveys will include questions about LCC behaviors including: number of LCCs used in the past
 week, butted out because they wanted to smoke less, and forgone), other tobacco use (OTP), blunt use, and quit
 intentions and attempts.)
- The weekly surveys will be sent out at 6am EST and will close 48 hours later. There will be a reminder email sent in the afternoon, and the next day.

Post-Test Survey: Day 21

- For the post-test on day 21, participants will be asked to complete a longer questionnaire about their current tobacco use and behaviors including current LCC smoking behavior, LCC nicotine dependence, OTP use, LCC and OTP quit intentions, and LCC and OTP quit attempts.
- Participants in conditions 1 and 2 will be asked recognition questions to assess whether they can recognize warnings shown to them in their condition
- Participants will also be asked about their study experience
- The post-test surveys will be sent out at 6am EST and will close 48 hours later. There will be a reminder email sent in the afternoon, and the next day.

Data Management

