Data management will be conducted by the study team. Multiple processes have been implemented to ensure high data quality, including internal pilots to test the protocol and ensure that data collection instruments are working properly, and ongoing data monitoring will be conducted during data collection to ensure that any issues with data quality are caught early and fixed. A pilot of the protocol with actual participants will be conducted before the full study is launched and participants will be asked about their experience in the study at the end of the pilot to further ensure that the protocol is working as intended and ensure a high quality data collection.

Statistical Methods

We will analyze the data using intention-to-treat analyses. Our primary outcome is LCC quit intention at post-test. We will model LCC quit intentions with message condition (warnings with images, FDA proposed text-only warnings, and a no warning control) as the between-participant predictor.

Analysis methods will depend on the time point that the outcome was measured. Post-test measures will be analyzed differently than repeated measures from the daily survey and weekly surveys, as outlined below. All models will include a categorical indicator of day to control for the durable linear effect of time.

Analysis methods for post-test measures will use linear regression for continuous outcomes, including the primary outcome of quit intentions, and logistic regression for dichotomous outcomes. Imputation will be used so that all participants who were randomized to an intervention and completed at least one daily survey will be included in the analysis, consistent with intention to treat practices.

Secondary models will examine differences between groups for items measured multiple times in either daily or weekly surveys (ex., LCC behavior measures). For these models, we will use linear mixed modeling to account for the repeated measure design. Mixed models are appropriate to use and robust to missing data, so we will be able to include everyone who completed at least 1 daily questionnaire, consistent with intention to treat practices.

Secondary models will also be run for the primary outcome as well as secondary outcomes that include the number of daily surveys completed (This is a measure that is equivalent to the dose of the stimuli for the active condition and also applies to the control condition)

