LCC behavior is collected separately for cigarillos and little cigars and will be combined in the main analyses for these outcomes (ex. Number of cigarillos in past day and number of little cigars in past day combined for number of LCCs in past day). We also plan to run separate analyses for cigarillo behavior and little cigar behavior.

Additional information about the statistical analysis can be found in the Statistical Analysis Plan.

Methods: Monitoring

To ensure maximum protection of human subjects, we submitted our research project information to the School of Medicine Data Safety and Monitoring Board at the University of North Carolina at Chapel Hill and asked them to make the final decision regarding risk to participants and whether or not our studies should receive their supervision. A representative of the board agreed that given that the study involves a low risk behavioral intervention in a healthy population, that oversight by the board was not necessary.

Adverse events are not expected in this trial due to the minimal risks to participants, and no threat to participant health, so plans for collecting, assessing and reporting adverse events are not necessary.

We have no plans for auditing trial conduct.

Ethics and dissemination

This trial was granted an exemption by UNC's IRB under IRB # 22-2531.

All protocol changes will be communicated to the study team, and any change in participant interaction will be approved by UNC's IRB. Protocol changes will be tracked in an appendix table with new versions after initial approval including the date, version number, and a summary of changes.

Consent

Consent will be collected electronically as part of the baseline survey at the beginning of the study. At the beginning of the baseline survey, participants will view the consent form with an agreement to participate in the study. Participants will only be able to proceed with the study if they agree to participate in the study.

Confidentiality

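### The primary day-21 quit-intention model, as written, leaves out the baseline quit-intention score; adding it would sharpen every contrast at no data cost

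*Combined protocol and SAP*

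**What the plan says.** Under Statistical Methods, the primary outcome is LCC quit intention at post-test, analyzed by linear regression: "We will model LCC quit intentions with message condition", with three levels (image warnings, FDA text-only warnings, no-warning control). Two other model terms are mentioned. One is general: "All models will include a categorical indicator of day to control for the durable linear effect of time". The other, the number of daily surveys completed, appears only in secondary models and is measured after randomization.

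Missing day-21 scores are handled by imputation: "Imputation will be used so that all participants who were randomized to an intervention and completed at least one daily survey will be included". The variables in the imputation model are not listed. The section closes by pointing elsewhere: "Additional information about the statistical analysis can be found in the Statistical Analysis Plan". The text of that plan is not part of the material supplied.

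The baseline score exists. The Methods Overview has participants at day 0 "complete a questionnaire about their tobacco use and behaviors (e.g., intentions and quit attempts) and other measures of interest". In Appendix B, the baseline column includes the Weekly Behavior Assessment, and that assessment contains the three LCC quit-intention items that make up the primary endpoint. The day-0 description under Data collection methods puts allocation after this: "At the end of the baseline questionnaire, survey software will randomly assign participants to one of the 3 study conditions".

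**The concern.** For an outcome analyzed at one day, a day indicator is a constant and drops out. Study arm is then the only working predictor in the primary model. A pre-randomization measurement on the same instrument as the endpoint is usually the strongest available predictor of it, and here everyone randomized should have one.

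Leaving it out does not bias the randomized comparison or inflate type I error. What is lost is precision. The hypotheses are specific contrasts (image versus text, image versus control, text versus control, both warning arms versus control), and some of these can have much less power than the three-group test.

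Timing also matters. The Allocation and Blinding section states "Researchers will not be blinded to the condition that participants had been assigned to". A covariate added after day-21 data had been seen would be open to the charge of selection, so it should be fixed in writing first.

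**Working it through.** **Inputs.** From the documents: α = 0.05, 80% power and f = 0.12 (Sample Size); at least 750 quality completes (Methods Overview); equal allocation (Allocation and Blinding), so 250 per arm. Assumed: the correlation r between baseline and day-21 scores, which the documents do not give, over 0.2 to 0.7. Also assumed: f = 0.12 is an unadjusted effect.

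**The plan's own figure.** The Sample Size section claims 80% power "to detect a small change in differences between our groups (f=0.12") but states neither N nor the test. For a three-group F test with 750 completes, the noncentrality is λ = N·f² = 750 × 0.0144 = 10.8 with 2 and 747 df, and power is 84.4%. The stated 80% needs 673, or 675 in equal arms. Since 675/0.90 = 750, an unstated 10% loss would explain the gap, although the protocol calls the 750 completes. The stated power is therefore not reproduced exactly, but it errs on the safe side.

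**Effect of adjustment.** With the baseline score in the model:

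- standard error ratio = √(1−r²)
- equivalent n per arm = 250/(1−r²)
- three-group test: λ = 10.8/(1−r²), with 2 and 746 df

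| r | SE ratio | SE reduction | Equivalent n per arm | λ | Three-group power |
|---|---|---|---|---|---|
| none (unadjusted) | 1.000 | – | 250 | 10.80 | 84.4% |
| 0.2 | 0.980 | 2% | 260 | 11.25 | 85.9% |
| 0.3 | 0.954 | 5% | 275 | 11.87 | 87.8% |
| 0.5 | 0.866 | 13% | 333 | 14.40 | 93.4% |
| 0.7 | 0.714 | 29% | 490 | 21.18 | 98.9% |

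**Pairwise contrasts.** These use the noncentral t distribution, 250 per arm, two-sided 0.05, with effect d/√(1−r²). The value of d depends on how f is read:

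- Two-group f: d = 2 × 0.12 = 0.24.
- One arm apart from two equal arms: d = 3 × 0.12/√2 = 0.255.
- Three equally spaced means, adjacent arms: d = 0.12 × √1.5 = 0.147.

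| d | Unadjusted | r = 0.2 | r = 0.3 | r = 0.5 | r = 0.7 |
|---|---|---|---|---|---|
| 0.24 | 76.4% | 78.0% | 80.2% | 87.1% | 96.3% |
| 0.255 | 81.1% | 82.6% | 84.6% | 90.7% | 97.8% |
| 0.147 | 37.5% | 38.8% | 40.5% | 47.4% | 63.2% |

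**Cost if the covariate is useless.** One residual degree of freedom. At r = 0 the loss is about 0.0002 percentage points of three-group power.

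**If imputation already uses the baseline score.** Part of the gain is then already in hand. Suppose a fraction m of outcomes is missing completely at random and is imputed by regression on baseline. In units of σ²/n per arm, the unadjusted variance is (1−r²)/(1−m) + r² and the adjusted variance is (1−r²)/(1−m).

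- r = 0.5, m = 0.3: 1.071 against 1.321; SE ratio √(1.071/1.321) = 0.90, a 10% reduction instead of 13%.
- r = 0.7, m = 0.5: 1.02 against 1.51; SE ratio 0.82, an 18% reduction instead of 29%.

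The missing fractions here are illustrative.

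**The case against.** The strongest objection is that the detail may sit in the Statistical Analysis Plan that the protocol cites, which is where covariates and imputation variables would normally be listed. That stands as a limit: the point is that the supplied text does not pre-specify the covariate, not that the sponsor will not use it.

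Second, nothing is wrong with the current model. It is unbiased, and the three-group test already exceeds its stated power. This also stands, and it is why the point is an improvement and not an error.

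Third, the size rests on an assumed r. At r = 0.2 the three-group gain is only 1.5 points (84.4% to 85.9%). And if f = 0.12 came from an estimate that was already baseline-adjusted, the power gains in the tables are counted twice. The documents do not settle this. In that case, though, the power basis would assume an adjustment that the written analysis lacks, which is itself a reason to add it.

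Fourth, the power figures assume 750 complete records, whereas the plan imputes day-21 scores for anyone with at least one daily survey. The reduction of √(1−r²) is exact only against an analysis that makes no use of baseline. As shown above, the gain shrinks if the imputation model includes the score, but it does not vanish.

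Last, a plan that names no covariates offers none to choose among, so unblinded researchers are not a fault in the present text. Agreed. It is a reason to record the addition early.

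**Conclusion.** The point holds as a free improvement. In the text supplied, the primary regression has study arm as its only effective predictor, while a pre-randomization score on the same three items goes unused. For r between 0.2 and 0.7, the standard error of every arm contrast would fall by 2% to 29% relative to an analysis that ignores baseline, and by less if imputation already draws on it. Three-group power would rise from 84.4% to between 85.9% and 98.9%, provided f = 0.12 is an unadjusted effect and 750 people complete.

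Adjustment does not rescue the weakest reading: with equally spaced means, adjacent-arm power is still only 63.2% at r = 0.7. Confidence is high on what the supplied text omits; the size of the gain is conditional on r.

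**What to change.** Confirm whether the SAP already names the baseline score. If it does, repeat that in the protocol's Statistical Methods. If not, before day-21 data are examined:

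- State the primary model as day-21 quit intention on condition plus baseline quit-intention score (ANCOVA).
- Name the baseline score as a variable in the imputation model.
- For the repeated-measures models, say whether the day-0 value enters as a covariate, as a response or not at all, and adjust for the baseline value of the same measure where it is collected. Self-reported learning is measured only at day 21, so it has none.
- As tidying only, drop the day indicator from single-time-point models.

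The core change takes one or two sentences. It needs no new data and no further participants, and it uses one model degree of freedom.

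### The repeated smoking outcomes are to be analysed without their baseline values, although the baseline survey collects them; for the LCC counts this gives up substantial power

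*Combined protocol and SAP*

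**What the plan says.** The Statistical Methods section separates two sets of outcomes: "Post-test measures will be analyzed differently than repeated measures from the daily survey and weekly surveys, as outlined below".

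- For the post-test: "Analysis methods for post-test measures will use linear regression for continuous outcomes", and "logistic regression for dichotomous outcomes".
- For the rest: "Secondary models will examine differences between groups for items measured multiple times in either daily or weekly surveys (ex., LCC behavior measures"). For these, "we will use linear mixed modeling to account for the repeated measure design". No distribution or link is given by type of outcome.

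The predictors named in the section are message condition, a categorical indicator of day and, in further models, the number of daily surveys completed. A baseline value is not among them.

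Under Outcomes, the repeated secondary measures include "Number of LCCs smoked in past day (each day"), the number of LCCs in the past week, "Number of days smoked LCCs in past week (days 7, 14, and 21"), butting out, forgoing, and "LCC quit attempts (days 7, 14, and 21"). Appendix B puts the Weekly Behavior Assessment in the baseline column as well as at days 7, 14 and post-test. That assessment holds past-week LCC numbers and days, past-day items, quit intentions and quit attempts. Randomisation comes at the end of the baseline questionnaire.

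**The concern.** People differ far more in how much they smoke than a warning is likely to change it. Eligibility admits both every-day and some-day users, which widens that spread. In an unadjusted model the spread between people sits in the error term of the arm comparison. Averaging over 18 daily reports does not remove it, because it is a stable difference between people. A pre-randomisation measure of the same behaviour would remove much of it.

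At stake is the trial's evidence on smoking behaviour, as distinct from intentions. A null result on LCC numbers could reflect an inefficient analysis and be read as absence of effect. Because the counts are skewed and cannot fall below zero, the scale of the model is a second, smaller question.

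**Working it through.** **The plan's own figure.** No power is stated for any repeated outcome. The only figure is 80% at f = 0.12, α = 0.05, for the primary outcome. With 750 completes in three groups, λ = f²N = 0.0144 × 750 = 10.8 and the omnibus F test has 84.4% power (80% needs N = 673). That is a separate matter. It is used here only for the arm size, 750 / 3 = 250.

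**Inputs.** From the documents: 250 per arm and 18 daily reports. Assumed, because the documents give nothing: mean 2 LCCs per day in control, 1.6 with warnings (20% fewer), within-person gamma-Poisson variation with gamma variance 0.5, and complete data.

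**Step 1: unadjusted linear test, stable habits.** In a balanced random-intercept model the arm test is the t test of person means. With c² the squared coefficient of variation of person rates, the variance of a person's mean in an arm with mean m is

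V(m) = m²c² + [m + 0.5·m²(1 + c²)] / 18, and z = 0.4 / √{[V(2) + V(1.6)] / 250}.

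- Lognormal rates, log-SD 1.0 (c² = e − 1 = 1.718): V = 7.286 and 4.681, SE = 0.2188, z = 1.83, power Φ(1.83 − 1.96) = 45%. Simulation gave 47.3%.
- Gamma rates, variance 1 (c² = 1): V = 4.333 and 2.791, SE = 0.1688, z = 2.37, power 66%. Simulation gave 65.2%.

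In the first case 6.873 of the control variance of 7.286 is between people (4 × 1.718).

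**Step 2: add a baseline covariate.** If the baseline correlates r with the person mean, the residual variance is multiplied by 1 − r², so z becomes z / √(1 − r²).

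| r | lognormal, log-SD 1.0 | gamma, variance 1 |
|---|---|---|
| 0 | 45% | 66% |
| 0.5 | 56% | 78% |
| 0.7 | 73% | 91% |
| 0.8 | 86% | 98% |

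At r = 0.7 the gain equals multiplying the sample by 1 / (1 − 0.49) = 1.96.

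**Step 3: simulation with moderate drift in each person's rate after baseline.** Drift lowers the unadjusted power and weakens the baseline.

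| | linear | linear + baseline | log scale | log scale + baseline |
|---|---|---|---|---|
| lognormal, log-SD 1.0 | 39% | 73% | 57% | 91% |
| gamma, variance 1 | 54% | 84% | 47% | 88% |

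Across the spreads of person rates tried, the linear test rises from 26-58% to 60-86% (lognormal) and from 33-74% to 67-92% (gamma). Type I error stayed near 5%. Inverting Step 2, r = √[1 − (z₀/z₁)²] with z = Φ⁻¹(power) + 1.96. For 39% to 73%, z goes from 1.68 to 2.57 and r = 0.76. For 54% to 84%, z goes from 2.06 to 2.95 and r = 0.72. Pairing the ends of the two ranges gives r from 0.63 to 0.80. The drift runs therefore amount to assuming a baseline correlation of that order.

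**Step 4: what the choice of link does by itself.** Without baseline, the log scale gains under lognormal rates (57% against 39%) and loses under gamma rates (47% against 54%). A log-link GEE, which compares the same arm means, differs from the linear test by at most about 3 points. For three yes/no reports of a quit attempt (15% against 21%), linear and logit GEE tests both have 77.4% power at random-intercept SD 1 and both 65.4% at SD 2. For days smoked out of 7 both have 48.3%. The linear test rejected in 3.7-6.4% of null trials.

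**The case against.** A reader might infer three stronger claims, and the documents support none of them.

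- *The linear mixed model is invalid for counts.* At 250 per arm its type I error is near 5%, and a difference in mean LCCs is a legitimate target.
- *The linear model by itself wastes power on every repeated outcome.* Step 4 shows no loss for days smoked or quit attempts. For counts the sign depends on an assumed distribution of person rates that the documents do not give.
- *The linear rule contradicts the plan's logistic rule.* The logistic rule is written for post-test measures only, the plan says the two sets are handled differently, and nothing states that quit attempts are yes/no. What remains is an ambiguity: day 21 is both the post-test and one of three repeated occasions, so a yes/no value could fall under either rule.

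Other objections have some weight. The log-scale figures in Step 3 stand in for a fitted count model. A log-link random-intercept model (Poisson-lognormal) was also fitted, assuming stable habits and lognormal rates. Adjusted for a baseline weekly count, it had 99% power against 93% for the adjusted linear test at log-SD 1.0, and 98% against 84% at 1.2. Under gamma rates the two were level after adjustment (99% and 98%). Negative binomial regression on person totals showed gains for weekly counts, but with type I error of 6.8-8.2%, so those gains are not clean. The count model is thus a secondary change.

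The stated hypotheses concern quit intentions and learning, so these are supporting outcomes. The protocol also points to a Statistical Analysis Plan for more detail. No separate text of it is in the document reviewed, so a baseline covariate may be specified there. Nor can the baseline be assumed to enter as one of the repeated occasions: the listed days are 7, 14 and 21, and day 0 is not among them.

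**Conclusion.** The point holds for the repeated LCC counts. As written, their models leave out a baseline measurement that every randomised participant should have and that assignment cannot have affected. Under the assumptions shown, adding it raises the power of the planned linear test by roughly 20 to 35 points for a 20% reduction (58% to 86% and 39% to 73%, for example; less, 74% to 92%, where power is already high). The direction does not depend on the assumed shape of person rates. The size does, and it also depends on the baseline correlation, the mean and the effect. Missing surveys and the third arm are not modelled.

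Once baseline is included, the log scale was higher in the drift runs under both shapes, which supports a log-link count model without making it essential. No power claim is made for days smoked or quit attempts. The primary day-21 analysis is outside this point.

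**What to change.** 1. Adjust the model for each repeated outcome for its own baseline value from the Weekly Behavior Assessment, and name the item. For the daily count, say whether it is the past-day or the past-week number; the stable-habit runs with a fitted count model used a weekly count. In a log-link model enter it on the log scale, with a small constant for zeros.
2. For numbers of LCCs per day and per week, use a baseline-adjusted log-link count mixed model, with GEE and robust standard errors as the stated fallback. Report the model-based mean difference beside the ratio. Keep the baseline-adjusted linear mixed model with robust standard errors as a sensitivity analysis.
3. State whether quit attempts are yes/no. If so, use one logistic mixed model for days 7, 14 and 21, so that day 21 is not analysed under two rules.
4. If the separate Statistical Analysis Plan already settles any of this, bring the protocol text into line with it.

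The cost is wording and a few lines of code, with no new data. The downsides are a ratio as the main scale for the counts and possible convergence problems. Fixing the choice before outcomes are examined matters because the researchers are not blinded to condition.
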